2.8.1 Adverse events (AEs)

In the frame of safety analysis the following treatment-emergent AE types will be considered:

- Any AE
- Study treatment related AE
- AE leading to study treatment discontinuation
- Serious AE (SAE)
- Study treatment related SAE
- SAE leading to study treatment discontinuation
- Death

- RMP risks

All AE tables will be summarized by treatment group.

The Medical Dictionary for Regulatory Activities (MedDRA) version 24.0 or later will be used to code all AEs to a system organ class (SOC) and a preferred term (PT).

An overview table of the number and percentage of patients having each type of AE will be given. Crude incidence and exposure adjusted incidence rates will be provided (see [Section 5.4.3](#) [safety analysis]).

Tables with number and percentage of patients having particular AE summarized by treatment group, SOC and PT will be provided for all AEs listed above except for death. Summaries will be provided for each AE type separately.

For AE type ‘any AE’ tables with number and percentage of patients having particular AE summarized by treatment group, SOC, PT and maximum severity will be provided.

The SOCs will be presented in the alphabetic order and PTs will be ordered within the SOCs by decreasing order of frequency in the secukinumab treatment group.

If a patient reported more than one AE with the same PT, the AE with the greatest severity will be presented. If a patient reported more than one AE within the same primary system organ class, the patient will be counted only once with the greatest severity at the system organ class level, where applicable.

All AEs, deaths, SAEs and AEs leading to permanent treatment discontinuation and leading to study discontinuation and AEs related to COVID-19 will be listed separately. In addition an ocular AE listing with laterality will be provided.

Table 2-4 Overview of analyses on some safety endpoints

Analysis period	AEs & SAEs	AEs by maximum severity	Study treatment related AEs	Notables for vitals, lab criteria
Day 1 – Week 16	•Crude incidence	•Crude incidence	•Crude incidence	•Crude incidence
Entire study phase	•Crude incidence Exposure time adjusted incidence	•Crude incidence	•Crude incidence	•Crude incidence

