Study design	This is a randomized, placebo-controlled, double-blind, parallel-group, interventional, multicenter study in adult patients with moderate to severe TED. This study consists of the following 3 periods:
	Screening period (Week -6 to Baseline)
	Participants' eligibility will be assessed during the Screening period, which will occur for a maximum of 6 weeks.
	Treatment period (Baseline to Week 16)
	Eligible patients will be randomized in a 1:1 ratio to one of the following double-blinded treatment arms:
	1. Arm 1: Secukinumab 300 mg s.c. at Baseline, Week 1, 2, 3, 4, 8, 12 (n = 35)
	2. Arm 2: Placebo s.c. at Baseline, Week 1, 2, 3, 4, 8, 12 (n = 35)
	Patients will be stratified according to current smoking status (up to 20% smokers per arm) since smoking has a well-known impact on treatment efficacy in TED.
	Follow-up/open-label retreatment period (Week 16 up to Week 108)
	• Proptosis responders (see definition below) at Week 16 will be followed for relapse up to Week 68. If these patients relapse they will be offered a course of open label secukinumab at the time of relapse (see "proptosis relapsers" definition below).
	Proptosis non-responders (see definition below) at Week 16 will be     offered the option of open-label secukinumab treatment (with

	maintenance of blind of initial randomized treatment) for a duration of 16 weeks, i.e., up to Week 32 with last dose at Week 28, as follows:
	Open-label secukinumab 300 mg s.c. at Week 16, 17, 18, 19, 20, 24 and 28. Thereafter (i.e., from Week 32), patients will be followed up for a further 24 weeks
	For patients who are proptosis non-responders and who do not receive open-label secukinumab treatment, a follow-up visit 8 weeks after the Week 16 visit should be scheduled. At this follow-up Visit, the assessments associated with the Week 24 visit (for responders) should be performed.
	• Proptosis relapsers (see definition below) during the follow-up period (from Week 16 onward to Week 68) will be offered the option of retreatment with open-label secukinumab for a duration of 16 weeks (with maintenance of blind to initial randomized treatment) at the time of relapse as follows:
	Open-label secukinumab 300 mg s.c. at time of relapse, then at 1, 2, 3, 4, 8 and 12 weeks since time of relapse. Thereafter, patients will be followed up for a further 24 weeks (i.e., 40 weeks after start of retreatment) to assess safety.

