- 19. Women of childbearing potential, defined as all women physiologically capable of becoming pregnant, unless they are using effective methods of contraception during the study or longer if required by locally-approved prescribing information (e.g., 20 weeks in the European Union). Effective contraception methods include:

- Total abstinence (when this is in line with the preferred and usual lifestyle of the patient). Periodic abstinence (e.g., calendar, ovulation, symptothermal, post-ovulation methods) and withdrawal are not acceptable methods of contraception.
- Female sterilization (have had surgical bilateral oophorectomy with or without hysterectomy), total hysterectomy, or tubal ligation at least 6 weeks before taking study treatment. In case of oophorectomy alone, only when the reproductive status of the woman has been confirmed by follow-up hormone level assessment.
- Male sterilization (at least 6 months prior to Screening). For female patients on the study, the vasectomized male partner should be the sole partner for that patient.
- Barrier methods of contraception: condom or occlusive cap (diaphragm or cervical/vault caps). For countries where applicable, the use of spermicidal foam/gel/film/cream/vaginal suppository will be allowed.
- Use of oral (estrogen and progesterone), injected, or implanted hormonal methods of contraception or placement of an intrauterine device or intrauterine system or other forms of hormonal contraception that have comparable efficacy (failure rate < 1%); for example, hormone vaginal ring or transdermal hormone contraception.

In case of use of oral contraception, women should have been stable on the same pill for a minimum of 12 weeks before taking study treatment.

Women are considered post-menopausal and not of childbearing potential if they have had 12 months of natural (spontaneous) amenorrhea with an appropriate clinical profile (e.g., age appropriate history of vasomotor symptoms) or have had surgical bilateral oophorectomy (with or without hysterectomy), total hysterectomy or tubal ligation at least 6 weeks ago. In the case of oophorectomy alone, only when the reproductive status of the woman has been confirmed by follow-up hormone level assessment is she considered not of childbearing potential.

- 20. Past medical history record of infection with human immunodeficiency virus (HIV), hepatitis B or hepatitis C prior to Screening except for hepatitis C successfully treated and cured.

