2.5) To demonstrate that secukinumab is superior to placebo with regard to reduction in proptosis after 16 weeks of treatment.	2.5) Mean change from Baseline to Week 16 in proptosis in the study eye.
2.6) To demonstrate that secukinumab is superior to placebo with regard to improvement in disease severity after 16 weeks of treatment.	2.6) Mean change in EUGOGO disease severity from Baseline to Week 16.
2.7) To demonstrate that secukinumab is superior to placebo with regard to improvement in GO-QoL after 16 weeks of treatment.	2.7) Mean change from Baseline to Week 16 in GO-QoL score.
Safety (secondary) endpoint	Safety (secondary) endpoint
2.8) To evaluate the safety of secukinumab 300 mg s.c. compared to placebo.	2.8) Frequency of AEs, TEAEs, AEs resulting in treatment discontinuation, SAEs.

2 Statistical methods

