2.1.1.5 Safety endpoints

Discontinuation of treatment due to AE

Discontinuation of treatment due to AE is determined by the information given on the Adverse events eCRF page (action taken=“Drug withdrawn”). “Death” as a reason for treatment discontinuation will be summarized separately.

Treatment-emergent adverse events (TEAEs)

Treatment-emergent adverse events (TEAEs) are defined as adverse events (AEs) that occurred on or after the first dose of study treatment up to 84 days following the last dose of study treatment. In addition, AEs registered prior to start of double-blind treatment are considered as treatment-emergent if they have increased severity based on preferred term any time after the first dose of study treatment.

Serious adverse events (SAEs)

SAEs are determined by the flag on the Adverse Events eCRF page.

Treatment-related adverse event

Treatment-emergent adverse event is defined as treatment-related, if the investigator considered it as having a reasonable possibility to be related to study treatment, which is reflected in the eCRF with a corresponding flag.

Duration of exposure to AIN457 or Placebo (DBTP)

For calculations of exposure duration, last/ first dose date refers to receiving dose (prefilled syringe) > 0.

The duration of exposure to study treatment or placebo is computed as:

For patients completing the DBTP:

- Week 16 visit date – first dose date + 1.

For patients who discontinue treatment during DBTP:

- min (last dose date +84 days, Week 16 visit date) – first dose date + 1.

Duration of exposure to AIN457 (during entire study period)

For calculations of exposure duration, last/ first dose date refers to receiving dose (prefilled syringe) > 0. Duration of exposure will be defined as the time from first dose of study treatment to the time of treatment switch (for subjects who switch treatment) or minimum of (last dose of the treatment + 84 days) and (last visit date). Patients who switch treatment during the study (e.g., from placebo to active treatment) will have exposure to both medications using the appropriate start and stop dates (full details are described in Section 3.1 of the protocol [i.e. study protocol v01 dated 24-Aug-2021]).

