2.8 Safety analyses

Summaries may be performed separately for initial (Baseline to Week 16) period and entire study period (including follow-up). Week 16 is chosen due to the fact that patients may be switched to another treatment at this time. Use of data up to and including the last visit before first switch opportunity provides an unbiased comparison between AIN and placebo; data collected beyond Week 16 are included in analyses which summarize the entire study period.

All listings and tables will be presented by treatment group. Safety summaries include only data from the on-treatment period and follow-up period with the exception of Baseline data that will also be summarized where appropriate (e.g., change from Baseline summaries). The on-treatment period is defined as date of first treatment to (date of last treatment + 84 days).

In addition, a separate summary for death including on-treatment and post-treatment deaths will be provided.

In particular, summary tables for AEs will summarize only on-treatment events, with a start date during the on-treatment period (treatment-emergent AEs) for the DBTP and the entire study period.

Missing data will not be imputed for safety endpoints.

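### AE and SAE summary tables stop 84 days after the last dose, so for a retreated patient who completes the schedule the last 16 of 24 follow-up weeks enter none of them, although the safety endpoint is the frequency of AEs and SAEs as well as TEAEs

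*SAP*

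**What the plan says.** The endpoint for the safety objective, the same in Protocol Tables 2-1 and 2-2 and in SAP Table 1-1, is "Frequency of AEs, TEAEs, AEs resulting in treatment discontinuation, SAEs". AEs and TEAEs are named as separate quantities.

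SAP 2.8 opens broadly: "Safety summaries include only data from the on-treatment period and follow-up period". It then narrows the AE tables, for both the double-blind period and the entire study period: "summary tables for AEs will summarize only on-treatment events, with a start date during the on-treatment period (treatment-emergent AEs". The on-treatment period runs from first treatment to last treatment plus 84 days. SAP 2.1.1.5 gives TEAEs the same limit: "on or after the first dose of study treatment up to 84 days following the last dose of study treatment".

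SAP 2.8.1 introduces its list of tabulated types, which includes SAEs and treatment-related SAEs, with "In the frame of safety analysis the following treatment-emergent AE types will be considered". Table 2-4 then has a row for the entire study phase. SAP 5.4.3 censors exposure-adjusted rates at the earlier of end of observation and last dose plus 84 days. The disclosure tables in SAP 5.8 are also on-treatment or treatment-emergent.

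Outside the summary tables, SAP 2.8.1 lists all AEs and SAEs, and SAP 2.8 and 2.8.2 provide a death summary and listing that include post-treatment deaths.

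Protocol 12.5.2 contains the same on-treatment restriction on AE tables but gives no number of days. Its TEAE definition has no upper limit.

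**The concern.** The plan promises a frequency of AEs and SAEs and describes summaries that reach into follow-up, but the only AE and SAE frequencies it produces are treatment-emergent ones with an 84-day cut-off. A listing is not a frequency, because it has no denominator.

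The labelling adds to the problem. A reader of an incidence marked as entire study would take it to cover all the time patients were observed. For a retreated patient who completes the schedule it covers only the first third of post-course follow-up. An SAE that starts, say, 20 weeks after the last open-label dose would be absent from every SAE count and rate, although the schedule provides AE assessment at the visit that would record it.

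**Working it through.** Inputs:

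- Non-responders (SAP Table 2-2; Protocol Table 8-2): retreatment starts Day 113, last open-label dose Day 197 (NR28), course ends Day 225 (NR32), then visits on Day 281 (NR40) and Day 393 (NR56).
- Relapsers (Protocol Table 8-2, days since relapse): start Day 1, last dose Day 85 (R12), course ends Day 113 (R16), then visits on Day 169 (R24) and Day 281 (R40).
- AE assessment is scheduled at all of these visits.
- Window: last dose + 84 days. SAP 2.1.1.1 counts open-label doses in the last dose date.

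Step 1, reproduce the protocol's own figures of 40 weeks from start of retreatment and 24 weeks of follow-up:

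- Non-responders: 393 − 113 = 280 days = 40 weeks; 393 − 225 = 168 days = 24 weeks.
- Relapsers: 281 − 1 = 280 days = 40 weeks; 281 − 113 = 168 days = 24 weeks.

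Both agree with the protocol.

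Step 2, find where the window closes:

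- Non-responders: 197 + 84 = Day 281, the NR40 visit.
- Relapsers: 85 + 84 = Day 169, the R24 visit.

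Step 3, split the follow-up:

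- Non-responders: covered 281 − 225 = 56 days (8 weeks); not covered 393 − 281 = 112 days (16 weeks).
- Relapsers: covered 169 − 113 = 56 days (8 weeks); not covered 281 − 169 = 112 days (16 weeks).
- Share not covered: 112/168 = 67% on both tracks.

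Step 4, bound the total for this trial. SAP 1 reports 28 patients randomized and 23 in follow-up.

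- Ceiling, assuming all 23 were retreated, received every dose and reached NR56: 23 × 16 = 368 patient-weeks (23 × 112 = 2,576 days; 2,576/365.25 = 7.05 patient-years).
- A non-responder who declined open-label drug has the EOS visit at Week 24, Day 169 (Protocol 3). If the Week 12 dose was the last, the window closes on Day 85 + 84 = 169, so the gap is 0.
- A patient withdrawn at sponsor termination is handled as a premature withdrawal (Protocol 9.1.4), with an EOS visit 12 weeks after the last dose (Protocol 9.1.1). 12 × 7 = 84 days, so if that is the last contact the gap is again 0.

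The total therefore lies between 0 and 368 patient-weeks. The documents give no follow-up time per patient with which to narrow this.

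**The case against.** The strongest reply is that the restriction comes from the protocol. Protocol 12.5.2 sets TEAE-only tables in the same document that sets the endpoint, so the endpoint wording may simply be loose. This stands in part: the SAP does not depart from the protocol by tabulating on-treatment events, and a reader who inferred that it does would be wrong. It does not remove the mismatch between the endpoint and the tables, which both documents carry.

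An 84-day window is also a reasonable TEAE convention and fits the protocol's 12-week EOS visit after discontinuation. That stands, and the window need not change.

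Four stronger readings are tempting but unsupported:

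- That late events are lost. They are not: AEs and SAEs are listed without the window, and post-treatment deaths are summarised. With 28 patients and a purely descriptive analysis, the listings can be read directly.
- That 368 patient-weeks are excluded. This is a ceiling. Early termination makes it improbable.
- That the contraception text ("e.g., 20 weeks in the European Union") shows 84 days to be too short. Protocol 5.2 does not tie those weeks to the last dose or to attribution of adverse events, so the comparison should not be used.
- That the protocol states a safety purpose for the whole of this follow-up in the patients actually retreated. The clear statement, "patients will be followed up for a further 24 weeks (i.e., 40 weeks after start of retreatment) to assess safety", concerns relapsers. That group appears to be empty, because a relapser must first be a responder and SAP 1.2 reports none. For non-responders the corresponding text is incomplete, so the point rests on the AE assessments scheduled for them at NR40 and NR56.

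Finally, data beyond the window may be uneven. After early study discontinuation, AE monitoring is required for at least 30 days after the last dose (Protocol 10.1.1), and later SAEs go to the sponsor's safety group only if suspected to be related (Protocol 10.1.3). This is a fair limit on what an added table can show.

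**Conclusion.** The point holds as a reporting gap and an inconsistency in wording. The AE and SAE frequencies named in endpoint 2.8 are produced only for events within 84 days of the last dose, including in outputs labelled entire study, while SAP 2.8 says summaries include the follow-up period.

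The scheduled gap is exact: 16 of 24 weeks (67%) for a retreated patient who receives all doses and completes follow-up. The realised gap is unknown and probably much smaller than the ceiling. No treatment comparison depends on it, because superiority testing has been dropped. It is a cheap improvement to the completeness and labelling of the safety report and does not threaten the trial's conclusions.

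**What to change.** Keep the 84-day TEAE tables as they are. Then:

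1. Add to SAP 2.8.1 one descriptive table of all AEs and all SAEs with onset more than 84 days after the last dose and up to the last visit, by SOC, PT and treatment group. Label it as post-treatment. Show the number of patients observed beyond that point and their patient-time (from Day 85 after the last dose to the last visit). Add a footnote that collection after early discontinuation is less complete under Protocol 10.1.1 and 10.1.3.
2. Reconcile the wording: in SAP 2.8, state which summaries use follow-up data and which stop at the on-treatment limit; in Table 2-4, footnote the entire study phase row to say that its AE and SAE incidences end at last dose plus 84 days.

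The cost is one more table, from data already collected, and two wording edits. The table may hold few or no events. It will also have little or no comparator, since non-responders never retreated are scheduled to leave at about the point where the window closes. Even an empty table would show how much time was observed beyond the window, which the present outputs do not.

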1.1 Study design

This is a randomized, placebo-controlled, double-blind, parallel-group, interventional, multicenter study in patients with moderate to severe thyroid eye disease (TED). This study consists of the following 3 periods (see [Figure 1-1](#)):

Screening period (Week -6 to Baseline)

Patients' eligibility will be assessed during the Screening Period, which will occur for a maximum of 6 weeks. In the event of a major healthcare disruption (e.g., a pandemic or epidemic) that limits or prevents on-site visits to the study sites, the Screening Period may be extended to a maximum of 8 weeks before Baseline.

Double-blind treatment period (DBTP) (Baseline to Week 16)

Eligible patients will be randomized in a 1:1 ratio to one of the following double-blinded treatment arms:

- Arm 1: Secukinumab 300 mg s.c. at Baseline, Week 1, 2, 3, 4, 8, 12 (n=35)
- Arm 2: Placebo s.c. at Baseline, Week 1, 2, 3, 4, 8, 12 (n=35)

Patients will be stratified according to current smoking status (up to 20% smokers per arm), since smoking has a well-known impact on treatment efficacy in TED.

Follow-up/open-label retreatment period (Week 16 up to Week 108)

- Proptosis responders (see definition below) at Week 16 will be followed for relapse up to Week 68. If these patients relapse, they will be offered a course of open-label secukinumab at the time of relapse (see "proptosis relapsers" definition below).
- Proptosis non-responders (see definition below) at Week 16 will be offered the option of open-label secukinumab treatment (with maintenance of blind of initial randomized treatment) for a duration of 16 weeks, i.e., up to Week 32 with last dose at Week 28, as follows:

Open-label secukinumab 300 mg s.c. at Week 16, 17, 18, 19, 20, 24 and 28. Thereafter (i.e., from Week 32), patients will be followed up for a further 24 weeks [REDACTED].

For patients who are proptosis non-responders and who do not receive open-label secukinumab treatment, a follow-up visit (End of Study [EOS]) 8 weeks after the Week 16 visit should be scheduled. At this EOS visit, the assessments associated with the Week 24 visit (for responder) should be performed.

- **Proptosis relapsers** (see definition below) during the follow-up period (from Week 16 onward to Week 68) will be offered the option of retreatment with open-label secukinumab for a duration of 16 weeks (with maintenance of blind to initial randomized treatment) at the time of relapse as follows:

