2.8.4.2 Vital signs

Notable vital signs abnormalities will be analyzed by treatment group for the DBTP and the entire study period. A frequency table will be provided.

Normal blood pressure will be defined as systolic blood pressure (SBP) of 90 to < 120 mmHg, and diastolic blood pressure of 60 to < 80 mmHg under the measurement conditions outlined in the protocol. Notable blood pressure findings will be hypertension (SBP of ≥ 140 mmHg and/or diastolic blood pressure [DBP] of ≥ 90 mmHg) or hypotension (SBP of < 90 mmHg and/or a DBP of < 60 mmHg).

A normal pulse rate will be defined as a rate of 60 to 100 beats per minute (bpm). Notable pulse rate abnormality will be a rate below 60 bpm (bradycardia) or above 100 bpm (tachycardia).

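### Entire-study tables for severity, treatment-related AEs and notable values rely on crude incidence, although a retreated secukinumab patient is counted up to 2.5 times as long as a placebo switcher

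*SAP*

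**What the plan says.** SAP Table 2-4 sets out the safety summaries for two periods. For Day 1 to Week 16 all four columns show crude incidence. For the entire study phase, the column for AEs and SAEs shows "Crude incidence Exposure time adjusted incidence". The other three columns (maximum severity, treatment-related AEs, notable vital signs and laboratory values) show crude incidence only.

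The text of Section 2.8.1 differs. After introducing an overview of each AE type, a list that includes treatment-related AEs and treatment-related SAEs, it says: "Crude incidence and exposure adjusted incidence rates will be provided". For severity it promises only counts and percentages, "summarized by treatment group, SOC, PT and maximum severity will be provided". For vital signs, Section 2.8.4.2 says: "Notable vital signs abnormalities will be analyzed by treatment group for the DBTP and the entire study period".

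Two other rules fix how long a patient is counted. Section 2.8: "The on-treatment period is defined as date of first treatment to (date of last treatment + 84 days"). Section 2.1.1.5 ends exposure to the first treatment at the switch; patients who switch "will have exposure to both medications using the appropriate start and stop dates". Under Table 2-3, the entire-study AIN457 group is everyone randomized to secukinumab, including any open-label course. A placebo patient's events count under Placebo before the switch and under Any AIN457 after it.

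**The concern.** Crude incidence is the share of patients with at least one event, so it rises with observation time. Over the entire study, the design gives the groups unequal time. Non-responders in both arms may take a second course ("Open-label secukinumab 300 mg s.c. at Week 16, 17, 18, 19, 20, 24 and 28"). That course lengthens the AIN457 window of a secukinumab patient and closes the Placebo window of a placebo patient.

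The tables set AIN457 and Any AIN457 beside Placebo on severity, relatedness and notable values, which readers use to judge tolerability. If the underlying risks are equal, secukinumab will still show the higher percentages. The SAP already adjusts for exposure in one column of the same row and gives no reason for leaving out the others. Text and table also give a programmer different instructions for treatment-related AEs.

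**Working it through.** **Inputs from the documents.** Target days: Week 12 = Day 85 and Week 16 = Day 113 (SAP Table 2-1); NR28 = Day 197 (SAP Table 2-2). The window closes at last dose + 84 days (SAP 2.8) or at the switch (SAP 2.1.1.5). At termination 28 patients had been randomized, 25 had completed the double-blind period and 23 had entered follow-up (SAP 1).

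**Assumptions.** The same constant hazard in all groups (no drug effect); visits on target days; the same share *s* retreated or switched in each arm. The documents give no 16-week risk *q*, so a range is shown.

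**The plan's own figure.** The SAP states no exposure ratio. Its worked example in Table 5-1 can be reproduced: 100 days on placebo and an event on Day 110 give 110 − 100 = 10 days under Any AIN. The clock therefore restarts at the switch.

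**Step 1: windows.**
- Placebo switcher, under Placebo: 113 − 1 = 112 days.
- Secukinumab, full second course: 197 + 84 − 1 = 280 days.
- No open-label treatment, either arm: 85 + 84 − 1 = 168 days.
- Placebo switcher, under Any AIN457: 281 − 113 = 168 days.

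Ratio for a fully retreated patient against a switcher: 280/112 = 2.50.

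**Step 2: crude ratio for that pair.** Crude incidence over the longer window is 1 − (1 − q)^R with R = 2.5; divide by q.

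| q by Week 16 | Over 280 days | Crude ratio |
|---|---|---|
| 5% | 12.0% | 2.41 |
| 10% | 23.2% | 2.32 |
| 20% | 42.8% | 2.14 |
| 30% | 59.0% | 1.97 |
| 50% | 82.3% | 1.65 |
| 80% | 98.2% | 1.23 |

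**Step 3: whole groups at q = 20%.** Patients without open-label treatment have R = 168/112 = 1.5 and crude incidence 1 − 0.8^1.5 = 28.45%. Secukinumab: s × 42.76% + (1 − s) × 28.45%. Placebo: s × 20% + (1 − s) × 28.45%.

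| Share s | Mean days, secukinumab vs placebo | Time ratio | Crude ratio |
|---|---|---|---|
| 23/25 | 271 vs 116 | 2.33 | 2.01 |
| 23/28 | 260 vs 122 | 2.13 | 1.87 |
| 1/2 | 224 vs 140 | 1.60 | 1.47 |

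**Step 4: early termination.** If the secukinumab window is cut to 168 days, R = 1.5 and the ratio is 28.45/20 = 1.42. At 224 days, R = 2 and the ratio is (1 − 0.8²)/0.2 = 1.80.

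**Step 5: Any AIN457.** With equal arms, all fully retreated, half the group has 280 days and half 168. The mean is 224 days and the time ratio 224/112 = 2.0. The crude ratio is [(42.76 + 28.45)/2]/20 = 1.78.

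**Step 6: effect of the adjusted rate.** Section 5.4.3 divides patients with an event by total time to first event. At q = 20% the hazard is −ln(0.8)/112 per day, or 72.8 per 100 patient-years, whether follow-up is 112 or 280 days. The ratio is 1.00.

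**Step 7: number of checks.** From protocol Tables 8-1 and 8-2, scheduled post-baseline vital signs number 7 to Week 16 and 15 to NR40. Hematology and chemistry samples number 4 and 9.

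**The case against.** The strongest reply is that the SAP already knows of this problem. Section 2.8 explains that Week 16 was chosen because patients may then switch, and calls the data up to that visit an unbiased comparison. Crude tables for that period are planned in all four columns. This stands, and those tables need no change. What is missing is a matching caution on the entire-study tables.

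Four stronger readings are tempting, and the documents do not support them.

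- A reader might take 2.5 as the ratio between the arms. It holds for a fully retreated patient against a switcher. Open-label treatment was optional, placebo patients who did not switch run to about Day 169, and termination shortened windows by an amount not stated. Entering follow-up does not prove retreatment.
- A reader might infer that treatment-related AEs will never be exposure-adjusted. The 2.8.1 text promises adjusted rates at overview level, and Table 2-4 describes itself as covering only some endpoints. This is a conflict to reconcile.
- A reader might extend the point to all laboratory notables. Section 2.8.3 summarizes them by visit, and such summaries do not accumulate over unequal time. Only a cumulative crude table would be affected.
- A reader might turn the check counts into percentages of patients flagged. That needs a per-check probability, which the documents do not give, and independence between checks. Blood pressure and pulse tend to persist within a patient, so independence would exaggerate the gap.

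It is also fair that consequences are limited: SAP Section 3 makes all analyses descriptive, and 28 patients give sparse counts. But without tests, the displayed percentages are what the reader has to go on.

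**Conclusion.** The point holds in a limited form. In the entire-study row, crude percentages for severity, treatment-related AEs and cumulative notable values overstate secukinumab relative to placebo when hazards are equal. At a 20% 16-week risk the size is about 2.1 for the extreme patient pair, 1.5 to 2.0 for whole groups, and 1.4 to 1.8 if termination cuts the secukinumab window to 168 to 224 days. For Any AIN457 with full retreatment it is about 1.8. For the extreme pair it falls to 1.65 and 1.23 at risks of 50% and 80%.

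These figures rest on a constant hazard, visits on target days and equal shares retreated and switched. Actual windows are not in the documents. The conclusion does not extend to the Day 1 to Week 16 tables, to by-visit laboratory summaries, or to the AEs and SAEs column, which already has the adjusted rate. The conflict between text and table on treatment-related AEs needs correcting whatever the size.

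**What to change.** 1. In Table 2-4, entire-study row, add the Section 5.4.3 exposure-adjusted incidence for treatment-related AEs. This brings the table into line with the 2.8.1 text.
2. Extend the same rate to the severity and notable-value tables where an onset can be defined, for example time to first severe AE, or to the first visit with a notable vital sign. The definition must be written first: maximum severity may come from a later event than the first, and a notable value is dated only to the visit at which it was seen.
3. Where no onset is defined, footnote the entire-study crude table: groups differ in observation time by design, and comparison between arms is confined to Day 1 to Week 16.

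The cost is SAP wording, a little programming that reuses the rate routine already specified, and no new data. With 28 patients, rates by SOC, PT and severity will rest on few events and have wide intervals.
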